1.0 Study Summary

Study Title	AI-Enhanced App-based Intervention for Adolescent E-cigarette Cessation
Study Design	The design for this study will be a qualitative study based on individual interviews.
Primary Objective	To receive feedback from adolescents (n=30) on usability
Secondary Objective(s)	NA
Research Intervention(s)/ Investigational Agent(s)	NA
IND/IDE #	NA
Study Population	Adolescents from 14 to 20 years old who use e-cigarettes
Sample Size	30
Study Duration for individual participants	Each participant will spend approximately take 30 to 60 minutes to complete the interview, including 10 minutes consenting process. There is only one interview for each subject.
Study Specific Abbreviations/ Definitions	N/A

2.0 Objectives*

2.1 *Describe the purpose, specific aims, or objectives of this research.*

Response: The objective of this study is to develop an effective, user-friendly, app-based intervention for adolescents who use e-cigarettes. We will receive feedback from adolescents on the beta version of the app regarding: 1) functions, 2) design, and 3) content.

2.2 *State the hypotheses to be tested, if applicable.*

NOTE: A hypothesis is a specific, testable prediction about what you expect to happen in your study that corresponds with your above listed objectives.

Response: There are no hypotheses in this study.

3.0 Scientific Endpoints*

3.1 *Describe the scientific endpoint(s), the main result or occurrence under study.*

*NOTE: Scientific endpoints are outcomes defined before the study begins to determine whether the objectives of the study have been met and to draw conclusions from the data. Include primary and secondary endpoints. Some example endpoints are: reduction of symptoms, improvement in quality of life, or survival. Your response should **not** be a date.*

Response: When there is saturated theme regarding the adolescents' perspectives about the usability of the e-cigarette cessation app-based intervention.

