Response: This study has a one-time data collection point. We will conduct the usability survey and task performance test during the interview meeting. After the survey and task performance test, we will conduct the interviews. The audio recording and the transcripts will be obtained. In addition, the contact information, including name, phone number and email address, if they agree, will be collected to schedule the interviews.

12.3 List any instruments or measurement tools used to collect data (e.g. questionnaire, interview guide, validated instrument, data collection form).

Include copies of these documents with your submission.

Response: This will be semi-structured interview. The basic interview questions that will be used are included in the interview guide (attached). As part of the interview, we will ask participants to conduct specific tasks within the app and the prompt is included in the interview guide file. Further follow-up questions will be used for probing. In addition, we will conduct a brief survey using mHealth App Usability Questionnaire.

12.4 Describe any source records that will be used to collect data about subjects (e.g. school records, electronic medical records).

Response: NA

*12.5 Indicate whether or not **individual** subject results, such as results of investigational diagnostic tests, genetic tests, or incidental findings will be shared with subjects or others (e.g., the subject's primary care physician) and if so, describe how these will be shared.*

Response: Individual subject results will not be shared with subjects or others.

*12.6 Indicate whether or not **study** results will be shared with subjects or others, and if so, describe how these will be shared.*

Response: Study results will be shared via publication. Subjects or others may have access to published findings of the study.

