19.0 Data Management and Analysis*

19.1 Describe the data analysis plan, including any statistical procedures. This section applies to both quantitative and qualitative analysis.

Response: Quantitative data including demographic questions and survey questions will be analyzed with descriptive statistics. For the qualitative data from the interviews, a content analysis approach will be used with a deductive approach.

19.2 If applicable, provide a power analysis.

NOTE: This may not apply to certain types of studies, including chart/records reviews, survey studies, or observational studies. This question is asked to elicit whether the investigator has an adequate sample size to achieve the study objectives and justify a conclusion.

Response: No power analysis is needed.

19.3 Describe any procedures that will be used for quality control of collected data.

19.4 Response: data.

Response: Research team members will meet biweekly to check the research procedures and ensure the quality of the data.

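### Does entering theme saturation as the only endpoint in Section 3.1 leave the study without a usable outcome?

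*Protocol*

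**What the plan says.** The protocol's Section 3.1 asks for the main result or occurrence being studied. Its printed note explains that "Scientific endpoints are outcomes defined before the study begins to determine whether the objectives of the study have been met", and that they should also allow conclusions to be drawn. The whole response is "When there is saturated theme regarding the adolescents' perspectives about the usability of the e-cigarette cessation app-based intervention". No other endpoint is given anywhere in the protocol, and the Study Summary lists secondary objectives as not applicable.

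The objective appears twice. The Study Summary (Section 1.0) has "To receive feedback from adolescents (n=30) on usability". Section 2.1 has "We will receive feedback from adolescents on the beta version of the app regarding: 1) functions, 2) design, and 3) content", after an opening sentence about developing an effective and user-friendly app. Section 2.2 states that there are no hypotheses.

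On data, Section 12.2 says "We will conduct the usability survey and task performance test during the interview meeting", with interviews to follow. Section 12.3 names the mHealth App Usability Questionnaire, describes the app tasks as part of the interview, and adds that "Further follow-up questions will be used for probing".

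On analysis, Section 19.1 says "Quantitative data including demographic questions and survey questions will be analyzed with descriptive statistics" and, for the interviews, that "a content analysis approach will be used with a deductive approach". Section 7.1 sets recruitment at approximately 30, and Section 19.2 says that no power analysis is needed.

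**The concern.** Set against the form's own definition, the entry looks misplaced. Saturation means that further interviews add no new themes. It describes whether the data are sufficient and carries no information on what adolescents think of the app. Read literally, the endpoint would be met even if every theme were a complaint. It would then seem to say nothing about functions, design or content, which Section 2.1 sets out to learn.

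Three further features strengthen the impression:

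- The usability questionnaire and the task performance test both bear on usability, yet neither is entered as an endpoint, and Section 19.1 does not name the task test.
- Section 19.1 chooses deductive coding, while Section 12.3 plans probing that could bring out unanticipated feedback. If codes were fixed in advance, an absence of new themes could partly reflect the coding frame.
- Saturation appears only in Section 3.1. It is neither defined there nor tied to the target of about 30.

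If the criticism held in full, the study's only prespecified outcome would support no conclusion about the app, and the survey and task results would have no stated role.

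**Working it through.** The protocol has no alpha, power, effect size or sample size formula, so there is no figure to reproduce. The check is a comparison of sections.

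**1. Does the entry fit the objective?** The Study Summary's objective is to receive usability feedback, and Section 2.1 specifies three areas for it. Such an objective is met when the feedback is obtained and reasonably complete, favourable or not. Saturation bears directly on completeness. The Section 3.1 prompt also accepts an occurrence as well as a result. The entry therefore addresses whether the objective was met. It does not by itself supply the content from which conclusions are drawn.

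**2. Is the content named elsewhere?** Yes. The Section 3.1 sentence gives its subject as adolescents' views on usability, Section 2.1 lists the three areas, and Section 19.1 says how interviews and survey answers will be analysed. Together these identify the output as usability themes plus a descriptive summary of the questionnaire.

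**3. Would a reworded endpoint behave differently?** The natural alternative is the set of usability themes on functions, design and content.

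| | Saturation, as written | Usability themes, reworded |
|---|---|---|
| Interviews | about 30 | about 30 |
| Reported if all themes are complaints | yes | yes |
| Reported if all themes are praise | yes | yes |
| Instruments | unchanged | unchanged |
| Analysis in Section 19.1 | content analysis and descriptive statistics | the same |

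The alternative is just as neutral, which is proper for a study with no hypotheses. Neither wording would test the broader aim in the first sentence of Section 2.1.

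**4. Can the point be given a size?** Only on assumptions that the protocol does not supply. Suppose nine themes, each raised independently by a proportion p of participants, and read saturation as no new theme in the last 3 of 30 interviews. The chance that a given theme first appears in those 3 interviews is q = (1 − p)^27 × [1 − (1 − p)^3].

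- p = 0.10: q = 0.0581 × 0.271 = 0.0158, and (1 − q)^9 = 0.867.
- p = 0.20: (1 − q)^9 = 0.989.
- p = 0.30: (1 − q)^9 = 0.9996.

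Whether a theme is praise or complaint does not enter the formula, so the result is the same for both by construction. It shows no harm, and the conclusion does not rest on it.

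A second calculation favours the plan. If everyone affected by a problem mentions it, and participants are independent, the chance that it is never mentioned in 30 interviews is (1 − p)^30. That is 0.215 at p = 0.05, 0.042 at p = 0.10 and 0.001 at p = 0.20.

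**5. The task test.** Section 19.1 introduces its quantitative data with a word that marks examples, so the list is open. Section 12.3 treats the tasks as part of the interview, whose data Section 19.1 covers. Section 12.2 places the test before the interview, so that second reading is arguable. Either way, how task results are summarised is detail that a protocol commonly leaves to an analysis plan.

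**6. Deductive coding.** Three preset areas of feedback suit a deductive start. Section 19.1 does not say that the frame is closed, and saturation within preset categories is not a contradiction. Neither the coding frame nor the attached interview guide is available here, so a closed frame would have to be assumed.

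**The case for a change.** The strongest case for a change is that this is the protocol's only endpoint field and that, by the form's own definition, the entry is not an outcome. An endpoint should also support conclusions from the data, and reaching saturation supports none about the app. The choice of endpoint is made in Section 3.1, so an analysis plan cannot be relied on to supply it. The remedy would cost little beyond wording: name the themes, list the questionnaire and task results as descriptive endpoints, and keep saturation as a check on sampling.

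Part of this stands. The sentence is a condition where an outcome was asked for, and saying that the endpoint is the usability themes would be clearer. What does not stand is the inference that the study then lacks an outcome or would report something different. Low cost alone does not justify a change that alters nothing in the conduct, analysis or interpretation. Listing the questionnaire and task results under Section 3.1 would not change their collection or, for the questionnaire, its planned descriptive summary. Asking for codes to be added is a preference of method, since no stated rule forbids it.

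**Conclusion.** No change to the plan follows. Section 3.1 contains a wording slip: it gives a sufficiency condition where the form wanted an outcome, but it names the right subject. Read with Sections 1.0, 2.1 and 19.1, it leaves little doubt that the usability themes are the intended result. The size of the effect is zero on the sample size, the instruments, the estimates and the conclusions.

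This rests on two readings of the protocol. The first is that its objective is to gather feedback without testing a hypothesis, which Sections 1.0 and 2.2 state. The second is that analysts will report the content of the themes and not merely that saturation occurred, which Section 19.1 implies by planning a content analysis. A tidier sentence could be adopted at any later revision, but nothing depends on it.

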5.0 Study Design*

5.1 *Describe and explain the study design (e.g. case-control, cross-sectional, ethnographic, experimental, interventional, longitudinal, observational).*

Response: The design for this study will be a qualitative study based on individual interviews.

6.0 Study Intervention/Investigational Agent

6.1 *Describe the study intervention and/or investigational agent (e.g., drug, device) that is being evaluated.*

Response: NA

6.2 *Drug/Device Handling: If the research involves drugs or device, describe your plans to store, handle, and administer those drugs or devices so that they will be used only on subjects and be used only by authorized investigators.*

- *If the control of the drugs or devices used in this protocol will be accomplished by following an established, approved organizational SOP (e.g., Research Pharmacy SOP for the Control of Investigational Drugs, etc.), please reference that SOP in this section.*

Response: NA

6.3 *If the drug is investigational (has an IND) or the device has an IDE or a claim of abbreviated IDE (non-significant risk device), include the following information:*

- *Identify the holder of the IND/IDE/Abbreviated IDE.*
- *Explain procedures followed to comply with sponsor requirements for FDA regulated research for the following:*

Applicable to:			
FDA Regulation	IND Studies	IDE studies	Abbreviated IDE studies
21 CFR 11	X	X	
21 CFR 54	X	X	
21 CFR 210	X		
21 CFR 211	X		
21 CFR 312	X		
21 CFR 812		X	X
21 CFR 820		X	

Response: NA

7.0 Local Number of Subjects

7.1 *Indicate the total number of subjects that will be enrolled or records that will be reviewed locally.*

Response: Approximately 30 adolescents will be recruited.

7.2 *If applicable, indicate how many subjects you expect to screen to reach your target sample (i.e. your screen failure rate).*

Response: We expect that approximately 100 adolescents will be screened who will be recruited from diverse community settings.

7.3 *Justify the feasibility of recruiting the proposed number of eligible subjects within the anticipated recruitment period. For example, how many potential subjects do you have access to? What percentage of those potential subjects do you need to recruit?*

Response: Researchers will leverage the participation of community-based primary care offices using existing relationships developed by [name] in previous studies of low-income populations as well as potentially utilizing the Community Engagement team at the University at Buffalo's Clinical and Translational Science Institute. Researchers will primary target this population, and researchers will access potential subjects within the anticipated recruitment period.

This is an exploratory study. Thus, we are not exactly sure what percentage of those subjects will respond, but the researchers have some connections with local schools and community centers. We believe that this would be a feasible plan.

8.0 Inclusion and Exclusion Criteria*

8.1 *Describe the criteria that define who will be **included** in your final study sample.*

NOTE: This may be done in bullet point fashion.

Response: Response: Inclusion criteria includes:

Adolescents

- Age 14-20 years
- Current e-cigarette users (have used e-cigarettes [vaped] in the past 30 days)
- I-phone users
- Interested in participating in an e-cigarette use cessation program
- Able to read English.

8.2 *Describe the criteria that define who will be **excluded** from your final study sample.*

NOTE: This may be done in bullet point fashion.

Response: Exclusion criteria includes:

Participants

- Age <14 or >20 years
- Current non-e-cigarette users (who have not smoked in the past 30 days)
- Not I-phone users
- Not interested in participating in an e-cigarette use cessation program
- Not able to read English

8.3 2) *Indicate specifically whether you will include any of the following special populations in your study using the checkboxes below.*

NOTE: Members of special populations may not be targeted for enrollment in your study unless you indicate this in your inclusion criteria.

Response: Adolescents who are 14-20 will be included in this study.

- Adults unable to consent
- Individuals who are not yet adults (infants, children, teenagers)
- Pregnant women
- Prisoners

8.4 *Indicate whether you will include non-English speaking individuals in your study. **Provide justification if you will exclude non-English speaking individuals.***

*In order to meet one of the primary ethical principles of equitable selection of subjects, non-English speaking individuals may **not** be routinely excluded from research as a matter of convenience.*

In cases where the research is of therapeutic intent or is designed to investigate areas that would necessarily require certain populations who

may not speak English, the researcher is required to make efforts to recruit and include non-English speaking individuals. However, there are studies in which it would be reasonable to limit subjects to those who speak English. Some examples include pilot studies, small unfunded studies with validated instruments not available in other languages, studies with numerous questionnaires, and some non-therapeutic studies which offer no direct benefit.

Response: While subjects may speak other languages, they will all have sufficient command of English to be able to consent and participate in the interviews to communicate with English speaking researchers. This is a pilot study, which do not provide researchers with the capacity of communication in other languages.

9.0 Vulnerable Populations*

If the research involves special populations that are considered vulnerable, describe the safeguards included to protect their rights and welfare.

NOTE: You should refer to the appropriate checklists, referenced below, to ensure you have provided adequate detail regarding safeguards and protections. You do not, however, need to provide these checklists to the IRB.

9.1 *For research that involves **pregnant women**, safeguards include:*
NOTE CHECKLIST: Pregnant Women (HRP-412)

Response: N/A

N/A: This research does not involve pregnant women.

9.2 *For research that involves **neonates of uncertain viability or non-viable neonates**, safeguards include:*
NOTE CHECKLISTS: Non-Viable Neonates (HRP-413), or Neonates of Uncertain Viability (HRP-414)

Response: NA

N/A: This research does not involve non-viable neonates or neonates of uncertain viability.

9.3 *For research that involves **prisoners**, safeguards include:*
NOTE CHECKLIST: Prisoners (HRP-415)

Response: NA

N/A: This research does not involve prisoners.

9.4 *For research that involves **persons who have not attained the legal age for consent to treatments or procedures involved in the research (“children”)**, safeguards include:*
NOTE CHECKLIST: Children (HRP-416)

Response: We will include participants who are below 18. We reviewed the checklist. We expect that there will be minimal risks involved in this research.

We will provide explanation to minimize the risks, such as breaches of confidentiality, and will make an effort to prevent those risks.

N/A: This research does not involve persons who have not attained the legal age for consent to treatments or procedures (“children”).

9.5 For research that involves *cognitively impaired adults*, safeguards include:
NOTE CHECKLIST: Cognitively Impaired Adults (HRP-417)

Response: NA

N/A: This research does not involve cognitively impaired adults.

9.6 Consider if other specifically targeted populations such as students, employees of a specific firm, or educationally or economically disadvantaged persons are vulnerable. Provide information regarding their safeguards and protections, including safeguards to eliminate coercion or undue influence.

Response: Contact information of Institutional Review Board will be provided during the consenting and interview processes to ensure their safeguards and protections, particularly for adolescents. Information regarding their safeguards to eliminate coercion or undue influence will be provided. Anytime when they do not want to participate in this study, they will be able to withdraw anytime, and this will be emphasized.

10.0 Eligibility Screening*

10.1 Describe screening procedures for determining subjects' eligibility.

Screening refers to determining if prospective participants meet inclusion and exclusion criteria.

Include all relevant screening documents with your submission (e.g. screening protocol, script, questionnaire).

Response: When the potential participants contact the researchers via mail, email, phone calls, program directors, research team members will make an appointment for an interview. Before making an appointment for an interview, researchers will determine participants' eligibility by asking the following questions via email, phone calls, or text:

To adolescents:

- How old are you? (To screen if they are between 14 and 20 years old)
- Are you a current e-cigarette user? (Yes to the following question, “Have you used an electronic vaping product such as PuffBar, ElfBar, Lost Mary, JUUL, Vuse, e-cigarettes, vapes, vape pens, e-cigars, e-hookahs, hookah pens, or mods at least 1 day in the last 30 days?”)
- Are you an iPhone user?

- Can you read English?
- N/A:** There is no screening as part of this protocol.

11.0 Recruitment Methods

- N/A:** This is a records review only, and subjects will not be recruited. NOTE: If you select this option, please make sure that all records review procedures and inclusion/exclusion screening are adequately described in other sections.

11.1 Describe when, where, and how potential subjects will be recruited.

NOTE: Recruitment refers to how you are identifying potential participants and introducing them to the study. Include specific methods you will use (e.g. searching charts for specific ICD code numbers, Research Participant Groups, posted advertisements, etc.).

Response: The PI will oversee all study recruitment and enrollment activities. To recruit participants who are 18 or older than 18, researchers will recruit potential participants through those listed in the IRB approved large research registry of families (Buffalo Research Registry [BRR] via email, mail, and phone. In addition, flyers will be distributed to healthcare settings, such as local free clinics, primary clinics, urgent care, retail clinics, WIC office, and Medicaid offices, as well as other non-healthcare settings, such as grocery stores, malls, cafeteria, libraries, universities, and churches, and youth community centers with permission from the establishment. Moreover, social network sites such as Facebook, Twitter, Instagram, Snapchat, LinkedIn will be considered for recruitment to broaden the reach, and the flyers will be posted in their original format. University at Buffalo sites will be used and a new account will be created for this study. Study flyers will be posted on the websites or online discussion boards which adolescent e-cigarette users may frequently use. We will distribute the flyers through the listserves at the universities. The study team will utilize the University at Buffalo's Clinical and Translational Science Institute (CTSI) for recruitment assistance and consultation. The CTSI's Recruitment Team provides resources and guidance on appropriate recruitment strategies, and assistance in linking our study team with community partners to effectively reach recruitment goals and target populations.

We will be also working with the Clinical and Translational Science Institute (CTSI) Community Engagement Team (CET) to create awareness of the study through their professional and community contacts. The tools they have available may include the Buffalo Research Registry (BRR, IRB Approved STUDY00000806), the Patient Voices Network (PVN), the Conventus CTSI/PVN and Evergreen Research Tables, i2b2 and TriNetX, Department of Emergency Medicine Research Assistant Program, and conducting outreach at various community events. These tools are methods by which the CET distributes IRB-approved recruitment information to community members. Through networks of CTSI, this study can be introduced to eligible participants of other research being conducted at University at Buffalo. In addition, we will announce

our study through ResearchMatch.org site. ResearchMatch.org is a national electronic, web-based recruitment tool that was created through the Clinical & Translational Science Awards Consortium. Thus, volunteers who registered on the ResearchMatch site will be able to see the announcement about our study.

To recruit participants who are younger than 18 years old, we will mainly recruit participants from schools and hospitals. We want to ask the staff at the hospitals and schools to introduce the app and this study to the potentially eligible participants who attend their schools or hospitals. We will contact the personnel, including school nurses of local middle and high schools in and around the Buffalo area, such as Heim Middle School and Amherst Middle School, to request permission to distribute the fliers.

11.2 Describe how you will protect the privacy interests of prospective subjects during the recruitment process.

NOTE: Privacy refers to an individual's right to control access to him or herself.

Response: When adolescents are interested in participating in the study by promotion flyer, they can directly contact the research team. When researchers are communicating with potential participants via phone or in person, the communication will be occurring at a private place. In that way, other people will not overhear or witness research activities. When we advertise the study via social media, comments will be shut off to protect participants' confidentiality and privacy. When participants contact the researchers through ResearchMatch site, their contact information will be shared with the research team only when they choose to do so. Participants will then have the option of replying yes or no through a set of quick links available in the notification. If a participant choose to respond in the affirmative, they will authorize ResearchMatch to release their contact information.

11.3 Identify any materials that will be used to recruit subjects.

NOTE: Examples include scripts for telephone calls, in person announcements / presentations, email invitations.

 For advertisements, include the final copy of printed advertisements with your submission. When advertisements are taped for broadcast, attach the final audio/video tape. NOTE: You may submit the wording of the advertisement prior to taping to ensure there will be no IRB-required revisions, provided the IRB also reviews and approves the final version.

Response: Recruitment materials are attached.

